### 3 INVESTIGATIONAL PLAN

#### 3.1 Overall Study Design and Plan

[figure not shown]
This is a Phase 2, randomized, double-blind, placebo-controlled, dose-finding study to assess the efficacy, safety, tolerability, PK, and PD of orally administered vadadustat in Japanese subjects with anemia secondary to NDD-CKD.

The study has a planned enrollment of 48 subjects to be enrolled at approximately 25 sites in Japan. There will be 16 subjects in each of the 3 tablet-count groups.

An overview of the study design is presented in [Figure 1](#).

Figure 1: Overview of Study Design

\* For subjects who develop an excess Hb response during the primary efficacy period, the number of tablets of study drug will be decreased (see Section 8.2.4). For these subjects, the number of tablets of vadadustat initiated at the Week 6 visit will be lower than indicated.

The study will include the following periods:

- Eligibility screening period (up to 4 weeks)
- Primary efficacy period (6 weeks; Weeks 1 to 6)
- Dose adjustment and maintenance period (10 weeks; Weeks 7 to 16)
- Follow-up period (2 weeks; Weeks 17 and 18)

Subjects will participate in a screening period (4 days to 4 weeks) to determine study eligibility, and eligible subjects will be randomized following the screening period.

Using a central randomization system, subjects will be randomized 1:1:1 to receive 1, 2, or 4 tablets at their baseline visit (Day 1). Within each tablet-count group, subjects will be randomized 3:1 to receive vadadustat (150, 300, or 600 mg vadadustat) or placebo. See the protocol section 8.2.2 for information regarding the randomization scheme.

Study drug treatment will be administered during a 6-week primary efficacy period. See the protocol section 8.2.4 for information on study drug administration. The primary efficacy period includes fixed-dose treatment to establish a dose-response relationship. However, if Hb level increase rapidly or if the Hb level exceeds 13.0 g/dL, the study drug dose can be decreased or interrupted (see the protocol section 8.2.4).

After completing the primary efficacy period, subjects will continue to a 10-week dose adjustment and maintenance period (see the protocol section 8.2.5). Subjects receiving placebo will be switched to vadadustat, and study drug dose will be adjusted to achieve a target Hb of 10.0-12.0 g/dL based on dose adjustment guidelines (see the protocol section 8.2.5).

Vadadustat treatment will stop after the dose adjustment and maintenance period has been completed (Week 16) and subjects will continue in a 2-week follow-up period (Week 17-18).

The clinical and safety assessments will be performed as described in the protocol section 9.3 and as listed in the protocol Appendix A.

## **3.2 Efficacy and Safety Variables**

### **3.2.1 Efficacy and PD Variables**

The following variable is the primary efficacy variable:

- Change from pre-treatment in Hb at Week 6.

The following efficacy endpoints will also be analyzed:

- Actual values and change (absolute and percent) from pre-treatment in Hb, hematocrit, RBC count, and reticulocyte count (both absolute and percent)
- Actual values and change (absolute and percent) from pre-treatment in iron, TIBC, TSAT, ferritin, and hepcidin

### **3.2.2 Safety Variables**

The following variables are the safety endpoints:

- AEs
- Vital signs
- ECGs
- Laboratory parameters

### **3.2.3 PK Variables**

The following variables are the PK variable:

- Pre-dose plasma concentrations of vadadustat at the Week 4 visit
- Pre-dose plasma concentrations of vadadustat's metabolites at the Week 4 visit

## **4 STATISTICAL METHODS**

### **4.1 Data Quality Assurance**

All tables, figures and data listings to be included in the report will be independently checked for consistency, integrity and in accordance with standard PAREXEL procedures.

### **4.2 General Presentation Considerations**

'Pre-treatment' of Hb is defined as the average of 2 Hb values obtained prior to treatment based on the qualifying screening Hb value and the Hb value at the Baseline Visit. 'Pre-

treatment' for other variables is defined as the last available pre-treatment assessment. In general, this is the value at the Baseline Visit. 'End of Treatment (EOT)' is defined as the assessment on the EOT form labeled as 'Week 16 Visit', even if other values closer to Day 113 are available. 'Treatment Day' will be calculated relative to start of dosing at Baseline Visit (i.e. Treatment Day = Assessment Date - Baseline Visit Date + 1).

Continuous data will be summarized in terms of the mean, standard deviation (SD), median, minimum, maximum and number of observations, unless otherwise stated. The minimum and maximum will be reported to the same number of decimal places as the raw data recorded in the database. The mean and median will be reported to one more decimal place than the raw data recorded in the database. The SD will be reported to two more decimal places than the raw data recorded in the database. In general, the maximum number of decimal places reported shall be four for any summary statistic.

Categorical data will be summarized in terms of the number of subjects providing data at the relevant time point (n), frequency counts and percentages. Any planned collapsing of categories will be detailed in the SAP text and the data displays.

Percentages will be presented to one decimal place. Percentages will not be presented for zero counts. Percentages will be calculated using n as the denominator. If sample sizes are small, the data displays will show the percentages, but any textual report will describe frequencies only.

Changes from baseline in categorical data will be summarized using shift tables where appropriate.

P-values greater than or equal to 0.001, in general, will be presented to three decimal places. P-values less than 0.001 will be presented as "<0.001".

Confidence intervals will be presented to one more decimal place than the raw data.

All report outputs will be produced using SAS® version 9.3 or a later version in a secure and validated environment. All report outputs will be provided to the Sponsor in a single Microsoft Word 2010 [Version 14.0] document.

### 4.3 Study Subjects

#### 4.3.1 Disposition of Subjects

A clear accounting of the disposition of all subjects who enter the study will be provided, from screening to study completion.

The summary of the following subject disposition will be presented.

- A summary of the number of subjects randomized, the number and percentage of subjects treated (with at least one dose of study medication) and the number and percentage of subjects completed through Week 6 Visit and discontinued by Week 6 Visit by treatment group and overall (Analysis population: All Subjects)

Randomized). For final analysis, a summary of the number and percentage of subjects completed Week 18 Visit and discontinued from the study by treatment group and overall will be provided (Analysis population: All Subjects Randomized). Withdrawals from the study will also be summarized by major reason.

By-subject listings of eligibility details, randomization details, visit dates and withdrawal/study completion details (including reason for discontinuation and duration of treatment prior to discontinuation) will be provided.

#### **4.3.2 Protocol Deviations**

Major protocol deviations are defined as those deviations from the protocol likely to have an impact on the perceived efficacy and/or safety of study treatments. The impact of major protocol deviations on the efficacy and/or safety results will be evaluated prior to unblinding to determine which data and/or subjects, if any, to exclude from the analysis populations (see Section 4.4),

Protocol deviations and any action to be taken regarding the exclusion of subjects or affected data from specific analyses will be determined in Protocol Deviation Specification document 20170207 version 2.0.

The protocol deviation will be summarized as following:

- A summary of the number and percentage of subjects with a protocol deviation by treatment group and overall and by type of deviation and by period (Analysis population: All Subjects Randomized)

A by-subject listing of protocol deviations will be provided.

#### **4.4 Analysis Populations**

Upon database release, protocol deviation and analysis population outputs will be produced and will be sent to Sponsor for review. An analysis population classification meeting will be arranged to discuss the outputs and to decide which subjects and/or subject data will be excluded from certain analyses. Decisions made regarding the exclusion of subjects and/or subject data from analyses will be made prior to unblinding and will be documented and approved by Sponsor.

The following summary of analysis population will be provided:

- A summary of the number and percentage of subjects allocated to each analysis population by treatment group and overall (Analysis population: All Subjects Randomized)

A by-subject listing of analysis population details will be provided. This listing will be presented by treatment group and include: site, subject identifier, inclusion/exclusion flag

for each population and reason for exclusion from each population. All subjects randomized will appear on this listing.

#### 4.4.1 Analysis Population for the Safety Analyses

The safety summaries and analyses will be based on the **safety population**. The safety population is defined as all enrolled subjects who receive at least 1 dose of study medication. In the event that a subject is allocated the incorrect study treatment as per the study randomization list, subjects will be summarized and analyzed ‘as treated’ i.e. by allocated treatment group.

#### 4.4.2 Analysis Populations for the Efficacy Analyses

The efficacy summaries and analyses will be based on the **modified intent-to-treat (MITT) population**. The MITT population is defined as all randomized subjects who have received at least 1 dose of study medication and have a pre-treatment Hb average defined as the average of the qualifying screening value and the baseline value, and at least one post-baseline Hb measurement. In the event that a subject is allocated the incorrect study treatment as per the study randomization list, subjects will be summarized and analyzed ‘as randomized’ i.e. by randomized treatment group.

For the efficacy variables, sensitivity analyses will be performed on the **per-protocol (PP) population** to assess the robustness of the study conclusions to the choice of analysis population. The PP population is defined as the subjects in the MITT population who have completed the study and have efficacy data through Week 6, have a study medication compliance of  $\geq 80\%$ , and do not have any major protocol deviations expected to significantly affect the primary efficacy endpoint. Subjects with major protocol deviations expected to significantly affect the primary efficacy endpoint will be identified and documented prior to data unblinding.

#### 4.4.3 Analysis Population for the PK Analysis

The PK summaries and analyses will be based on the **pharmacokinetics (PK) population**. The PK population is defined as all subjects in the safety population who have a pre-dose PK sample at Week 4. Subjects will be summarized and analyzed by actual treatment group.

#### 4.5 Demographic and Other Baseline Characteristics

The demographic and other baseline characteristics will be summarized for the MITT and safety populations. The following summaries will be provided:

- A summary of demographic variables (e.g. age, gender, weight, height and body mass index [BMI]) by treatment group and all subjects

- A summary of other relevant variables (e.g. estimated Glomerular Filtration Rate [eGFR] at baseline, CKD stage, etiology of CKD and smoking status) by treatment group and all subjects
- A summary of relevant medical history by treatment group and all subjects.
- A summary of prior and concomitant medications within 30 days prior to the first study drug dose up to and including Week 6 by treatment group and overall.
- For the final analysis, a summary of concomitant medications after Week 6 will be provided.

Age will be calculated as the number of complete years between a subject's birth date and the date of informed consent.

Definitions of eGFR and CKD stage are described in [section 4.8.4.7](#).

CKD stage will be determined by eGFR at baseline:

CKD stage	eGFR (mL/min/1.73m  )
1	90+
2	60 - 89
3a	45 - 59
3b	30 - 44
4	15 - 29
5	< 15

By-subject listings of demographic data and other baseline characteristics (as summarized above) will be provided

#### 4.6 Treatment Compliance

The treatment compliance will be summarized for the MITT and safety population. The following summary will be provided.

- A summary of the treatment compliance measures (i.e.  $\geq 80\%$  compliance and  $< 80\%$ ) by treatment group and study visit.

A by-subject listing of treatment compliance data will be provided.

#### 4.7 Efficacy Evaluation

##### 4.7.1 Analysis and Data Conventions

This study is designed to test for dose-response relationship. An analysis of covariance (ANCOVA) model will be used to compare absolute change from pre-treatment in Hb between the three vadadustat dosing groups and the placebo group. The model will include treatment assignment (3 dosed groups and one placebo group) and pre-treatment Hb value as a covariate. A step-down procedure will be used to control the overall type I error rate for the multiple comparisons. Testing of the highest dose compared with

placebo will be conducted first. If and only if this comparison is significant, then testing will proceed to comparison of the next lower dose and placebo, and so on. Therefore, no multiplicity adjustment will be needed for this analysis.

A linear regression dose-response modeling will be performed as a secondary analysis.

$$Y = \beta_0 + \beta_{dose}X$$

where Y is change in Hb and X is vadadustat dose.  $\beta_x$ s are parameters of the model.  $\beta_0$  is intercept and  $\beta_{dose}$  is slope, respectively.

The null hypothesis for the dose response will be that the regression coefficient of slope parameter is zero. The alternative hypothesis will be that the regression coefficient is not zero. Symbolically, this is expressed as follows:

$$H_0: \beta_{dose} = 0$$
$$H_1: \beta_{dose} \neq 0$$

This hypothesis will be tested using a 0.05 two-sided significance level.

#### 4.7.1.1 Multi-center Studies

Not Applicable. Analysis of center effect is not planned.

#### 4.7.1.2 Adjustments for Covariates

The primary efficacy analysis will be adjusted for the pre-treatment measure of primary efficacy variable.

An ‘unadjusted’ sensitivity analysis will be performed to assess the robustness of the study conclusion.

#### 4.7.1.3 Handling of Missing Data

For the MITT population analyses for the primary efficacy variable, the Last Observation Carried Forward (LOCF) approach will be used to impute missing data.

Subjects who underwent dose reduction before week 6 will not be analyzed differently from subjects who did not undergo dose reduction. This means we will use the actual Hb at week 6 for all subjects except the missing data, which will be carried from the last Hb before week 6 and after baseline.

- If a Baseline value is missing, the last value prior to baseline will be carried forward to the Baseline value but not to further values during the treatment period.
- For post-Baseline assessments, hemoglobin measurements at end of treatment and follow-up visits are not carried forward. Other than that, the most recent post-baseline assessments to the primary evaluation period (week 6) will be carried forward. Baseline and pre-Baseline values will not be carried forward to the post-Baseline visits.

For the secondary endpoint analyses, data will be used as observed and no imputation method will be used.

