#### Rescue therapy & ESA administration

Initiation of rescue therapy will be analyzed.

The following Rescue therapy summaries will be provided:

- A summary of the number and percentage of subjects requiring rescue with RBC transfusion from baseline to the end of the primary efficacy period (Week 6) and the end of the dose adjustment and maintenance period (Week 16)
- A summary of the number and percentage of subjects requiring rescue with ESAs from baseline to the end of the primary efficacy period (Week 6) and the end of the dose adjustment and maintenance period (Week 16). An ESA rescue is defined to fulfill the following 4 criteria simultaneously:

1. ESA administration, and
2. ESA administered because the subject experienced a clinically significant worsening of their anemia or symptoms of anemia, and
3. ESA administered because the subject's Hb level is <9.0 g/dL, and
4. **Subjects' reason for early study withdrawal is because of "Worsening of anemia requiring ESA rescue or blood transfusion".**

The following ESA administration summaries will be provided:

- A summary of the number and percentage of subjects requiring administration with ESAs from baseline to the end of the primary efficacy period (Week 6) and the end of the dose adjustment and maintenance period (Week 16)

The effect of treatment in terms of the proportion of subjects requiring with RBC transfusion / ESAs administration will be analyzed using Fisher's exact test. Three post-hoc pairwise comparison, i.e., Placebo vs 150 mg, placebo vs 300 mg, and placebo vs 600 mg, will be done.

By-subject listings of rescue therapies and ESA administration will be provided by treatment group.

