#### 4.10 Determination of Sample Size

The target enrollment will be approximately 48 subjects for the study with 12 subjects enrolled in each of the 4 treatment groups.

The study is powered based on a comparison of the highest dose vadadustat group (600 mg daily) and the placebo group. Based on the results from Study AKB-6548-CI-0005 that was conducted in the United States and evaluated vadadustat in patients with anemia secondary to NDD-CKD, it is assumed that the expected mean Hb changes from

baseline to Week 6 will be approximately 0 mg/dL for the placebo group and 1.35 g/dL for the highest dose vadadustat group (600 mg daily), with a common standard deviation of 0.68 g/dL across treatment groups. With these assumptions, the study with n=12 subjects per group will have >95% power to detect the difference between treatment group and control group, at 2-sided alpha of 0.05.

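### If Hb is still rising, LOCF shrinks the Week 6 dose-response estimate and the planned checks use completers only; the rules for early-withdrawal Hb and the Week 16 in-target rate also need fixing.

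*SAP*

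**What the plan says.** References are to the Amendment 3 text of the SAP.

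- **Primary endpoint (4.7.1.3, 4.7.2).** LOCF fills a missing Week 6 Hb. One sentence describes the missing data as values "which will be carried from the last Hb before week 6 and after baseline". A bullet below it says that "hemoglobin measurements at end of treatment and follow-up visits are not carried forward". Baseline values are not carried to later visits.
- **Checks.** Section 4.7.2 adds a complete-case analysis at Week 6. The per-protocol population (4.4.2) also requires efficacy data through Week 6.
- **MITT (4.4.2).** One post-baseline Hb, from any visit, is enough.
- **EOT (4.2).** End of treatment is whatever stands on the EOT form labelled Week 16 Visit, even if another value lies closer to Day 113.
- **Secondary endpoints.** "For the secondary endpoint analyses, data will be used as observed and no imputation method will be used" (4.7.1.3). "Percentages will be calculated using n as the denominator" (4.2), where n counts subjects with data at that time point.
- **ESA rescue (4.7.3).** Four criteria must all be met. The fourth is that the subject's "reason for early study withdrawal is because of" worsening anaemia needing ESA rescue or transfusion. The transfusion-rescue summary carries no such criterion.

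**The concern.** The study exists to estimate a dose-response and choose a Phase 3 starting dose. Section 4.10 plans mean changes of "approximately 0 mg/dL for the placebo group and 1.35 g/dL" at 600 mg by Week 6. If that rise is gradual, a Week 2 or Week 4 value standing in for Week 6 is too low on active drug and roughly right on placebo, so both the contrasts and the regression slope shrink. The two planned checks cannot show which estimate to believe, because neither uses the earlier Hb of subjects who left.

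Two further rules are not settled. For completers, EOT and follow-up come after Week 6, so barring those values from LOCF can matter only for early withdrawals, and the SAP does not say which form those subjects' last visit goes on. At Week 16, as-observed data with subjects-with-data as denominator can remove ESA-rescued failures from the in-target percentage. That percentage is one of the endpoints for the maintenance objective.

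**Working it through.** **Inputs from section 4.10:** difference 1.35 g/dL; "with a common standard deviation of 0.68 g/dL across treatment groups"; 12 per arm; test "at 2-sided alpha of 0.05". **Assumed, because the SAP gives no figure:** linear rise from 0 to 1.35 g/dL over six weeks; share *f* of the arm carried forward; last value at week *w* = 2 or 4.

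**1. The plan's own figure.** Noncentrality = 1.35 / (0.68 × √(2/12)) = 4.86. With 22 df, power is 99.6%, which reproduces the stated >95%.

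**2. LOCF shift in the 600 mg mean.** Shift = −*f* × 1.35 × (1 − *w*/6).

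| *f* | *w* = 2 | *w* = 4 |
|---|---|---|
| 10% | −0.10 × 1.35 × 2/3 = −0.09 | −0.10 × 1.35 × 1/3 = −0.045 |
| 20% | −0.20 × 1.35 × 2/3 = −0.18 | −0.20 × 1.35 × 1/3 = −0.09 |

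If the same share is carried forward in every active arm, the slope shrinks by the proportion *f* × (1 − *w*/6): 6.7% to 13.3% from Week 2, and 3.3% to 6.7% from Week 4.

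**3. Effect on the 600 mg test.** Allowing for the extra spread from mixing visits, power with 1, 2, 3 or 4 of 12 carried from Week 2 is 98.9%, 97.4%, 94.8% or 91.1%. From Week 4 it is 99.4% down to 98.1%.

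**4. Alternative estimator.** Simulation used four arms of 12, visits at Weeks 2, 4 and 6, SD 0.68 and a linear rise; where the visit correlation was set explicitly it was 0.7.

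- 15% random dropout, true difference 1.35: LOCF 1.24 to 1.25, likelihood about 1.34.
- Anaemia-driven placebo dropout of about a quarter, assumed true difference 1.65 (not an SAP figure): complete-case 1.47 to 1.50, LOCF 1.65 to 1.68, likelihood 1.65 to 1.68.

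Ranges are across runs with different settings. LOCF is off in the first case and complete-case in the second; the likelihood estimate is close in both.

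**5. Which Hb is carried.** Take a subject who leaves before Week 6 and whose last Hb is on the EOT form.

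- The first sentence in 4.7.1.3 selects that Hb; the bullet excludes it.
- If it is the subject's only post-baseline Hb, the subject is in MITT (4.4.2), nothing may be carried forward, and no primary value exists.
- Using or excluding one such value that differs from the previous visit by 0.5 to 1.5 g/dL (assumed) moves an arm mean by 0.5/12 = 0.04 to 1.5/12 = 0.125 g/dL.

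If the last visit is not on that form, the bullet has no effect and there is no conflict.

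**6. Week 16 rate.** Suppose 8 subjects are in range and *k* of 12 withdrew without a Week 16 Hb.

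| *k* | As observed | Withdrawals not in target |
|---|---|---|
| 1 | 8/11 = 72.7% | 8/12 = 66.7% |
| 2 | 8/10 = 80.0% | 8/12 = 66.7% |
| 3 | 8/9 = 88.9% | 8/12 = 66.7% |

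**The case against.** LOCF is clearly specified, and the SAP gives neither a trajectory nor a dropout rate. Dose reduction for excess response (section 3.1) could flatten the rise, which would shrink the bias. In the anaemia-driven scenario LOCF is nearly unbiased. These points stand: the size depends on assumptions, and LOCF is not wrong under every mechanism. A reader might infer that the 600 mg test is in danger. The documents do not support that, because the bias there is toward no effect and power stays at or above 91% in the worst case computed.

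A reader might also take the two LOCF sentences as a flat contradiction. On the 4.2 definition, EOT is the Week 16 form, and the bullet can be read as an exception to the general rule. The conflict exists only if early withdrawals are recorded on that form. If they are, their Hb might be scored as Week 16 and they would not leave the denominator, so the LOCF conflict and the Week 16 denominator problem do not hold in full together. What remains is that each reading leaves one defect.

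Nor do the documents show that every rescued subject drops out of the rate. Withdrawal is part of the ESA-rescue definition, not of transfusion rescue, and the definition does not itself say that Week 16 Hb is absent. The Week 16 rate is descriptive, with the Fisher test at Week 6 (4.7.3). Counts and n are displayed, and rescue and withdrawals are tabulated separately. Counting all withdrawals as failures is a choice that also penalises withdrawals unrelated to Hb. These points limit the importance of the Week 16 rate but leave its scoring rule unstated.

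**Conclusion.** The concern holds in a limited form, and a change is advisable. If Hb rises roughly linearly, LOCF with 10-20% of the 600 mg arm carried forward lowers that arm's mean change by about 0.09-0.18 g/dL from Week 2 or 0.05-0.09 g/dL from Week 4, with proportionate shrinkage of the slope when all active arms are affected alike. That matters for estimating the dose-response, not for showing that 600 mg differs from placebo. The checks rest on Week 6 completers, while a better estimator is available from Hb already collected.

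The conflict over the carried-forward value is conditional on early-withdrawal Hb being on the EOT form. The Week 16 denominator effect is 6 to 22 percentage points in the example, for a descriptive endpoint, and applies to withdrawn subjects without a Week 16 Hb.

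**What to change.** 1. **Primary estimate.** Before unblinding, make a repeated-measures likelihood model the primary Week 6 estimate: all scheduled post-baseline Hb through Week 6, visit × treatment, visit × pre-treatment Hb. An unstructured covariance over three visits needs only six parameters. Keep LOCF-ANCOVA as a sensitivity analysis. If the primary analysis is already locked, add the model as a pre-specified sensitivity analysis instead.
2. **Eligible Hb.** Reconcile the two sentences in 4.7.1.3 by stating which pre-Week 6 Hb may be used and how early-withdrawal visits are labelled. Align the MITT definition in 4.4.2 with that rule, and state how any Hb taken after rescue is handled.
3. **Week 16 rate.** Use the MITT denominator and count subjects withdrawn or rescued before Week 16 as not in target. Do not score an early-withdrawal Hb as Week 16 merely because of the form label. Show the observed-case rate alongside.

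The cost is SAP wording and one more model on collected data. The Hb interval may widen slightly, and responder rates will look less favourable, including for withdrawals unrelated to Hb.
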